| | 
6.1 Thoroughly describe the study design.
 
This study consists of two phases. Phase 1 will be a randomized controlled trial (RCT). Having a controlled group is the gold standard to measure the efficacy of an intervention (Polit & Beck, 2021). RCTs provide the most persuasive evidence on whether one variable has a causal influence on another. RCTs' main strength is the certainty with which causal links may be determined. Kolb's learning theory serves as the underpinning for this study (Kolb & Kolb, 2009; Kolb, 1984).
 
Manipulation: The researcher will do a cold debriefing (after one-day post-simulation) for undergraduate nursing students in the intervention group.
 
Control: The control group will do a hot debriefing (immediately after the simulation).
 
Randomization: The researcher will assign the participants to a control or experimental based on number generator.
 
Once participants complete Phase 1, we will record their progress on REDCap. If they chose to only participate in Phase 1, we will mark their status as "completed" on REDCap. If they expressed interest in Phase 2, we will randomly select 16 participants from the pool based on a number generator and update their status on REDCap for Phase 2.
 
Outcome: The study outcome is BLS competence level. The competence level will be measured AHA (2020) BLS competency Checklist. First, the control and experiment groups will complete a pre-test on BLS competence. Both groups will do a pre-test. After finishing
 |

TEMPLATE: RESEARCH PROTOCOL

| NUMBER | ACTIVE DATE | PAGE |
|---------|-------------|----------|
| HRP-503 | 02-04-2020 | 10 of 40 |

the pre-test, we will do the randomization process. Then the intervention group will receive (cold debriefing); the control group will have the (hot debriefing). Both groups will do the post-test immediately after the debriefing session and another post-test after 24 hours of the first post-test.

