For phase 2, we will do a qualitative descriptive design with focus groups interview. Themes relating to hot and cold debriefing will be generated using a focused qualitative interview technique. Focused interviews are loosely structured interviews in which the interviewer guides the participant through a set of questions (Polit & Beck, 2021). Throughout the guide, participants are encouraged to share their own experiences and discuss all topics freely. Researchers can obtain all necessary information utilizing this technique, and participants will have the capability to provide illustrations and explanations (Polit & Beck, 2021).

6.2 Detail the procedures being performed, specifically the interaction or intervention with human subjects and/or their identifiable information. Please be clear and concise and provide information relevant to the current study. For example, please be sure that what will be done for this research is explained and differentiated from activities that have already taken place or will be submitted for future review. Please note that details about recruitment and consent are asked in later questions.

Potential participants will access the REDCap link to answer the eligibility questions (1) if they are above 18 years of age and (2) if they are senior or third year undergraduate nursing students. If they are eligible, they will enter their demographic on REDCap. After that, The PI will assign the participants to a hot or cold debriefing group based on a number generator. Participants will do a baseline BLS competence where they will do a simulation experience related to the competence of BLS, which is conducted as part of the study design. There will be a scenario about a nurse taking care of their client at a hospital, and when the nurse enters the client's room to check on their client, they find that their client is unresponsive. Nursing students are expected to start the process of Basic Life support. Nursing students are expected in the simulation to check the client's

TEMPLATE: RESEARCH PROTOCOL

| NUMBER | ACTIVE DATE | PAGE |
|---------|-------------|----------|
| HRP-503 | 02-04-2020 | 11 of 40 |

responsiveness, activate the cardiopulmonary arrest code, begin cardiopulmonary resuscitation, and give 30 compressions and 2 breaths. They will attach an automated external defibrillator and follow the instruction of the machine. The total scenario will last up to 5 minutes.

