Another interaction with participants will be the debriefing experiences, where students will do a group debriefing. Afterward, participants in the hot debrief group will do their post-test immediately after their debrief on the same day as the simulation, and another post-test after 24 hours of the first post-test. And then, the cold debrief participants will do the simulation, wait 24 hours, have the debrief, and will do an immediate post-test, and another post-test after 24 hours of the first post-test. The simulation will be conducted in order to complete the BLS assessment checklist at baseline, post-test, and second post-test. The same simulation and BLS Assessment checklist will be conducted at baseline, post-test, and second post-test. The BLS competence and DES will be administered online via REDCap. During the qualitative phase, participants will engage in a focus group which will be the final interaction. Random sampling will be used to select subsamples from both hot and cold groups for the focus group..

6.3 Describe procedures being performed to monitor subjects for safety or minimize risks.

The study carries minimal risk. Potential participants will not be expected to expose more than what they might face in a simulation experience that they are familiar with. Participants will be informed that they can choose to participate or not and can withdraw at any time. They can also decline to answer any questions that make them uncomfortable. The PI will receive training from the Co-PI/Faculty Advisor to monitor participants for any psychological stress during study phases. The PI and Co-PI/Faculty Advisor will meet weekly to discuss interactions with participants and ensure that the procedures for managing data protect confidentiality.

6.5 Where applicable, list and describe the data collection tools such as surveys, data collection forms, etc. All tools described should be uploaded in the RAP Smart Form on the Local Site Documents page unless they are standardized, validated tools.

For Phase 1

- (A) Demographic
- (B) BLS Competence Checklist

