| 9.0 STUDY TIMELINES | 
9.1 Describe the duration of an individual subject's participation in the study. List the number of study visits or frequency of study visits.
 
Phase 1:
 
The participants will be asked to fill in the demographic data (5 minutes). Baseline BLS Competence level (5 minutes). After that, PEARLS Healthcare Debriefing Tool will (10 minutes). After debriefing, students will complete a survey about their debriefing experience (10 minutes). Finally, a post-test BLS Competence level (5 minutes) and another post-test BLS Competence level after 24 hours for both groups (5 minutes).
 |

TEMPLATE: RESEARCH PROTOCOL

| NUMBER | ACTIVE DATE | PAGE |
|---------|-------------|----------|
| HRP-503 | 02-04-2020 | 16 of 40 |

| | |
|--|--|
| | 
Phase 2: 45-60 minutes of focus group interview.
 
9.2 Describe the timeline allotted for the enrollment of subjects. From 08/24/23 to 11/01/23
 
9.3 Describe the estimated date for the investigators to complete this study (complete primary analysis). We estimate that data analysis will be completed by May 1, 2024.
 |
| | 
10.1 Describe how subjects will be screened for eligibility.
 
The PI will ask permission from the student affairs office of the undergraduate nursing student to send an email to potential participants. Potential participants will be contacted via the UC email, and we will post flyers in the simulation lab at the CON. Potential participants will access the REDCap link or scan the QR code to answer the eligibility questions (1) if they are above 18 years of age and (2) if they are senior or third year undergraduate nursing students. The potential participant will also indicate in REDCap if they want to participate in phase 2 (focus group). In case there are over 16 participants who want to participate in phase 2, we will randomly choose 8 participants from the hot debriefing group and another 8 participants from the cold debriefing group. If they are eligible, they will enter their contact details, such as their name, email, and phone number(s) on REDCap. Alternatively, they may also contact the PI via email or phone. Once a potential participant's response is received, the PI will contact them to verify their eligibility and contact information.
 |
| | 
10.2 Describe/list the inclusion/exclusion criteria for the study. Senior or Third Year Undergraduate Nursing students who are above 18 years old.
 |

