| | 
13.1 Describe the amount, method, and timing of payments to subjects.
 
13.0 COMPENSATION FOR SUBJECTS
 
Phase 1:
 
-Hot Debriefing Participants:
 
Day One (Baseline, Immediate Debriefing, Post-Test): \$25 Amazon gift card will be sent via email after completing baseline.
 
Second Post-Test (after 24 hours of the first post-test): \$20 Amazon gift card will be sent via email after completing second post-test.
 
-Cold Debriefing Participants:
 
Day One (Baseline): \$25 Amazon gift card will be sent via email after completing baseline.
 
Following Day (Debrief and Post-Test): \$25 Amazon gift card will be sent via email after completing debrief and post-test.
 
Second Post-Test (after 24 hours of the first post-test): \$20 Amazon gift card will be sent via email after completing second post-test.
 
-Phase 2 (Qualitative Phase): \$25 Amazon gift card will be sent via email after completing the qualitative interview. Participants who choose to withdraw at anytime during the qualitative study will also receive a \$25 Amazon gift card will be sent via email.
 
Total for hot debriefing in phase 1 (\$45)
 
Total for cold debriefing in phase 1 (\$70)
 
Total of hot debriefing in phases 1 and 2 (\$70)
 
Total of cold debriefing in phases 1 and 2 (\$95)
 |

| | |
|--|--|
| | 
The cold debriefing group will need 3 days to complete phase 1, while hot debriefing will need only 2 days to complete phase 1.
 
Both the hot and cold debriefing groups have the same time for participation; however, the cold group will need to arrive 24 hours after the simulation experience. Participants in the cold group will require additional time for transportation and scheduling a different day for the research activity. Therefore, the PI will give an additional \$25 Amazon giftcard to compensate.
 |
|--|--|

| | |
|--|---|

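### Eligibility does not require availability for all visit days, so a student who cannot return on day 2 loses the first post-test and the DES only if allocated to cold debriefing

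*Protocol*

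**What the plan says.** Entry. Protocol 10.2 gives the whole criterion: "Senior or Third Year Undergraduate Nursing students who are above 18 years old". On the REDCap screen (6.2, repeated in 6.6, 10.1 and 12.1) students "answer the eligibility questions (1) if they are above 18 years of age and (2) if they are senior or third year undergraduate nursing students". Next, the investigator contacts respondents to confirm eligibility and contact details. Nothing asks whether a student can attend the visits.

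Schedule. In 6.2, "participants in the hot debrief group will do their post-test immediately after their debrief on the same day as the simulation", whereas "the cold debrief participants will do the simulation, wait 24 hours, have the debrief, and will do an immediate post-test". Section 9.1 adds "another post-test BLS Competence level after 24 hours for both groups" and places the DES after the debriefing. Section 13.1 sums up: "The cold debriefing group will need 3 days to complete phase 1, while hot debriefing will need only 2 days to complete phase 1". It also says "Participants in the cold group will require additional time for transportation and scheduling a different day for the research activity", and pays the cold arm $25 more ($70 against $45).

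Allocation. Section 6.1 randomises after finishing "the pre-test, we will do the randomization process". Section 6.2 assigns the arm before baseline. Both orders come before day 2.

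Analysis. Protocol 17.1 and the SAP use independent t-tests for the between-arm comparisons of BLS competence (hypothesis 1b) and DES (hypothesis 2), and name no time point for the former. Sections 14.1 and 14.3 treat refused parts as missing. Section 11.2 allows one 15% attrition figure, not split by arm.

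**The concern.** The days required by cold contain the days required by hot and add one. One characteristic present before randomisation, a timetable that rules out the next day, can therefore decide whether an outcome exists, and it does so differently by arm. Students with that characteristic stay in the hot comparison and drop out of the cold one. A two-sample t-test on those observed then compares groups that randomisation made alike but attendance did not.

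The protocol knows of the burden. Section 13.1 pays for it, and section 2.1 lists extra scheduling and reassembling the students among the drawbacks of cold debriefing. Because the debriefing is a group session (6.2), moving one student is awkward. A late cold debriefing would also fall outside the one-day interval in 6.1, and no visit window is stated to catch it.

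**Working it through.** **1. What each student contributes** (baseline done on day 1; schedule from 6.2, 9.1 and 13.1)

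| Student cannot attend | Measure | Hot | Cold |
|---|---|---|---|
| Day 2 | First post-test, DES | observed (day 1) | missing on schedule |
| Day 2 | Second post-test | missing | missing on schedule |
| Day 3 only | First post-test, DES | observed | observed (day 2) |
| Day 3 only | Second post-test | observed (day 2) | missing |

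Day-2 unavailability is differential for the first post-test and the DES. It is not differential for the second post-test, where the extra cold loss comes only from students unavailable on day 3. Giving the DES online does not help, because a cold student absent on day 2 has no debriefing to rate.

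**2. The plan's own numbers.** Section 17.1 gives 26 per group, raised to 30. 26 × 1.15 = 29.9, so 30 (60 in total); dividing instead, 26 / 0.85 = 30.6, so 31 (62 in total). The 26 is reproduced by a two-sided t-test at 5%, 80% power and d = 0.8 (25.5, so 26). It is not reproduced from the stated eta squared of 0.25, which gives 13 per group by t-test. So d = 0.8 below is an assumption.

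**3. Power with loss in cold only** (first post-test or DES). Two-sided t-test at 5%, noncentrality = d × √(n₁n₂/(n₁+n₂)). For 30 v 24: 0.8 × √(720/54) = 2.92 on 52 degrees of freedom.

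| Hot v cold | Cold loss | Power at d = 0.8 |
|---|---|---|
| 30 v 30 | 0 | 86.1% |
| 30 v 26 | 4 (13%) | 83.5% |
| 30 v 24 | 6 (20%) | 81.8% |
| 30 v 21 | 9 (30%) | 78.7% |
| 30 v 18 | 12 (40%) | 74.8% |

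The 30 v 21 row puts all of the planned attrition (60 × 0.15 = 9) in the cold arm. The loss rates are assumptions.

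**4. Power with equal loss** (second post-test, day-2 unavailability): 82.2% at 10%, 80.0% at 15% and 71.6% at 30% lost from each arm.

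**5. Bias among those observed.** If a share q of cold students is lost, and their mean differs by δ SD from the rest, the cold mean among those observed shifts by q × δ SD while the hot mean does not. With no true effect, the rejection rate of a nominal 5% test is:

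| q | δ (SD) | Bias (SD) | Rejection rate |
|---|---|---|---|
| 10% | 0.5 | 0.05 | 5.4% |
| 15% | 1.0 | 0.15 | 8.5% |
| 30% | 1.0 | 0.30 | 17.9% |

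Neither q nor δ is in the documents. The table shows a range and is not an estimate; the sign of δ is unknown too.

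**The case against.** A reader might infer that students who cannot return the next day can fail the primary comparison in the cold arm alone. The documents do not support that. The hot arm must also return on day 2 for its second post-test, so such a student is incomplete for phase 1 in either arm, and for any complete-case repeated-measures analysis of hypothesis 1a. Nor is there a named primary comparison: section 5.1 defines the primary endpoint as completion of phase 1, and neither document fixes a time point for hypothesis 1b. The asymmetry is certain only for the DES and the first post-test.

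Other objections have weight:

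- The information sheet is given before the baseline activity (23.1), and the consent discussion (24.1) covers what participation involves. Since both schedules need day 2, a student who knows that day is impossible has reason to decline. This lowers the likely number, but it is self-selection and not an entry rule.
- The extra $25 is an incentive to attend the cold arm's added visit. It does not free a student who has a class or clinical placement.
- Bias requires attendance to be related to BLS or DES scores, and nothing in the documents shows that it is.
- The documents give no laboratory hours, so no figure can be put on start days lost to weekends.

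What remains is that the criteria admit such students, allocation precedes the visit that separates the arms, and the planned t-tests do not correct for arm-dependent loss.

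**Conclusion.** The point stands as a cheap improvement to the design. It does not show that the comparison is invalid. Attendance can make missingness depend on arm for hypothesis 2, and for hypothesis 1b if that is tested at the immediate post-test. At the second post-test, cold needs one more day than hot.

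The effect on power is modest: about 82% at 30 v 24, assuming d = 0.8, and below 80% in the 30 v 21 case. Bias is the greater worry. Under the assumed inputs it runs from negligible (0.05 SD) to material (0.30 SD), and the documents cannot say where in that range the trial lies.

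**What to change.** Add to 10.2 and to the REDCap screen, for every student and before allocation, a criterion such as: available to attend on three consecutive days. Have the investigator book all three slots when verifying eligibility, before the arm is known; hot students then release the third. Hold baseline sessions only on days from which both schedules can be completed. Because the rule is the same for everyone and precedes allocation, it cannot itself unbalance the arms.

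Two related clarifications would help: name the time point for hypothesis 1b, and reconcile the two accounts of when randomisation takes place (6.1 and 6.2) so that screening and booking clearly come first.

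Cost: one screening question, a booking rule, a few students screened out and fewer start days. Section 3.1 gives 183 + 204 = 387 students, of whom 60 are needed (60/387 = 15.5%). Even on the 183 quoted in 17.1, 60 is about a third (32.8%).

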| | There are a total of 183 senior undergraduate nursing students and 204 third year undergraduate nursing students. Based on G*Power 3.1, the recommended sample size will be 26 participants in each group. Still, because there is a possibility that participants may withdraw from the study, the total number will be 30 participants in each group. |
| | 
3.2 Describe the time that you will devote to conducting and completing the research, i.e. percent effort.
 |
| | The PI will devote 100 percent of his time to this study. |
| | 
3.3 Describe the availability of medical or psychological resources that subjects might need as a result of an anticipated consequences of the human research.
 |

TEMPLATE: RESEARCH PROTOCOL

| NUMBER | ACTIVE DATE | PAGE |
|---------|-------------|---------|
| HRP-503 | 02-04-2020 | 7 of 40 |

at any time, they can. In case of persistent stress or discomfort, the students' wellbeing center is ready to help them.

3.4 Describe your process to ensure that all persons assisting with the research are adequately informed about the protocol, the research procedures, and their duties and functions.

All members of the study team will be required to complete the web-based University of Cincinnati Collaborative Institutional Training Initiative (CITI) program. Additionally, the study team will be informed about the study protocol, the research procedures, and personnel's respective duties and functions. The study team will meet at least once bi-weekly to discuss the study progress. The study team will sign a conflict-of-interest form and provide their current CITI certification

3.5 Describe the facilities you have access to that will allow you to conduct the research.

The setting of the study will be held in the simulation Lab at the University of Cincinnati (UC) College of Nursing (CON). The CON has a large skills lab comprised of three rooms located on the 1st floor and a simulation collaboratory located on the 3rd floor.

The PI has a private office at the CON with telephones for subject enrollment and laptop computers using Microsoft Office Software and JMP statistical software. The laptops are connected to the UC Academic Health Center Server and is internet accessible. The PI has access to a secure computer research server for data storage. There is convenient access to facsimile transmission, e-mail, and photocopying equipment. Administrative assistance is also available.

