| | 10.5 If the research involves or may involve individuals who are students or employees where the research is taking place, please describe additional safeguards included to protect their rights and welfare. The academic performance will not be impacted if they choose not to participate. The primary PI is not a faculty member at UC-CON and has no direct relationship with participants. They will not be expected to expose more than what you might face in a simulation experience that they are familiar with. In case they feel uncomfortable or distressed in the study, they can stop, take a break, and re-join. If they want to withdraw at any time, they can. In case of persistent stress or discomfort, the students' wellbeing center is ready to help them. |
| | 11.1 Indicate the total number of subjects to be accrued. The total number of subjects to be accrued is 60 senior or third year undergraduate students. |
| | 11.2 If applicable, distinguish between the number of subjects who are expected to be enrolled and screened, and the number of subjects needed to complete the research procedures. We will over-recruit and enroll (60 potential participants) to account for 15% attrition. |

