| 17.0 DATA MANAGEMENT AND CONFIDENTIALITY | 17.1 Describe the data analysis plan, including any statistical procedures or power analyses. |
| | For quantitative phase 1, Statistical power G*Power 3.1 was used to determine sample size based on a 2-tailed, two-way repeated measure ANOVA for the design, a type I error of 0.05, a statistical power of 80% (type II error), and a large effect size of eta square .25-.99 (Faul et al., 2007). Based on the literature, a large effect size is appropriate for the use of simulation (Padilha et al., 2019; Pauly-O'Neill, 2009). Based on G*Power 3.1, the recommended sample size will be 26 participants in each group. Still, because there is a possibility that participants may withdraw from the study, the total number will be 30 participants in each group. There is a total of 183 eligible participants. |
| | 
Statistical Plan
 
The statistical analysis will be used by JMP Pro 16 software. The descriptive analysis for students' demographics will be computed to describe means, standard deviations, and frequencies. For hypothesis 1a, the appropriate statistical analysis test will be the repeated measure ANOVA to find the difference between the experimental and control group in pre and post-intervention. For hypothesis 1b, an independent t-test will be used to find the differences between the two groups in the BLS competence level. The p-value of <0.05 will be considered statistically significant, and the confidence interval will be set at 95%. If the p-value is less than 0.05, we will reject the null hypothesis; If the p-value is more than 0.05, we will fail to reject the null hypothesis. For hypothesis 2, an independent t-test will be used to compare means between hot debriefing and cold debriefing groups. DES with P-values <0.05 will be considered statistically significant.
 |

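### Enrolling 60 falls one completer short of the protocol's own target at its stated 15% attrition; it covers about 13%

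*Protocol*

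**What the plan says.** Protocol sections 3.1 and 17.1 give the same base figure: "Based on G*Power 3.1, the recommended sample size will be 26 participants in each group". Both then raise it because students may withdraw, so that "the total number will be 30 participants in each group". Neither section gives an attrition rate or shows how 26 became 30.

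Section 11.1 gives the overall figure: "The total number of subjects to be accrued is 60 senior or third year undergraduate students". Section 11.2 is the only place that attaches a rate to the margin: "We will over-recruit and enroll (60 potential participants) to account for 15% attrition".

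The SAP gives no sample size and no attrition allowance, so the protocol is the only source on this point.

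**The concern.** Attrition acts on the students enrolled. For 60 to account for a 15% loss, 85% of 60 should be at least the 52 that the protocol asks for, and it is not. The sentence in 11.2 is therefore not true of the protocol's own numbers, and a reader checking the sample-size justification will find this with one multiplication.

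At stake is the accuracy of the stated margin. Section 11.2 is where the template asks how many students must finish the study. The answer does not give that number, and the rate it offers does not lead to it.

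**Working it through.** **Inputs, all from the protocol**

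- Required per group: 26, so 2 × 26 = 52 in total (sections 3.1 and 17.1)
- Enrolled per group: 30, so 2 × 30 = 60 in total (sections 3.1, 11.1 and 17.1)
- Attrition: 15% (section 11.2)

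**Reproducing the planned 60**

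No formula is given, so the two usual ones were tried.

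| Formula | Per group | Total |
|---|---|---|
| n × (1 + 0.15) | 26 × 1.15 = 29.9, rounds to 30 | 52 × 1.15 = 59.8, rounds to 60 |
| n / (1 − 0.15) | 26 / 0.85 = 30.6, rounds up to 31 | 52 / 0.85 = 61.2, rounds up to 62 |

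Multiplying by 1.15 returns the plan's 30 and 60 exactly. Dividing by 0.85 is what preserves 52 completers after a 15% loss, and it gives 62.

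**What 60 delivers**

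- Expected completers at 15%: 60 × 0.85 = 51, or 30 × 0.85 = 25.5 per group
- Shortfall: 52 − 51 = 1 student
- Largest loss that leaves 52: 60 − 52 = 8, and 8 / 60 = 13.3%. Keeping 26 in each group also needs the losses to split 4 and 4.
- Check on the alternative: 62 × 0.85 = 52.7, at or above 52

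**Size of the effect on power**

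This needs an effect size and a test that return 26 per group, and the documents do not supply that pair. Section 17.1 sizes the trial "based on a 2-tailed, two-way repeated measure ANOVA for the design", with "a large effect size of eta square .25-.99". An assumption that does return 26 is a two-sided independent t-test at alpha 0.05, 80% power and a standardised difference d = 0.8, which solves to 25.5 per group, rounded up to 26. On that assumption:

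| Completers | Power |
|---|---|
| 26 and 26 | 80.7% |
| 26 and 25 | 79.9% |
| 25 and 25 | 79.1% |

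One missing student costs about 0.8 percentage points, and two cost about 1.6.

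Other readings of the sizing statement give very different requirements. They assume two groups, two or three measurements and a within-student correlation of 0.5, which the protocol does not state.

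- Repeated-measures ANOVA at eta squared 0.25 needs about 8 to 20 students in total, so 51 would be ample.
- Reading 0.25 as Cohen's f needs 28 to 34 in total for a within or interaction effect.
- The same reading needs 86 to 98 in total for a between-group effect, which neither 51 nor 52 would reach.

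On none of these readings is the difference between 51 and 52 completers important.

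**The case against.** The strongest reply is that this is a common add-15% shortcut with a trivial result. The plan's 60 differs from the strict 62 by two students, and the expected completers miss the target by one. All of that stands, and it limits how much weight the point can carry. It does not make the sentence in 11.2 correct, because 15% of 60 is 9 losses and the margin holds only 8.

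A reader might go further and infer that the trial is underpowered. The documents do not support that. The only power loss that can be calculated from a base of 26 per group rests on an assumed d = 0.8, and it is under one percentage point. The sizing statement itself names a different analysis and a different effect measure. Nor does the protocol promise that power survives attrition; it says only that the margin is there because students may withdraw.

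A reader might also be struck by a binomial calculation. If each student independently has a 15% chance of dropping out, both groups keep at least 26 of 30 with probability only about 28%. The protocol sets no such criterion, and the figure does not isolate the error: with 31 per group it is still only about 47%. Most of the gap is ordinary variation around an expected value, and it should not be used to size this problem.

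Finally, it can be said that lowering 15% to 13% merely fits the rate to the chosen enrolment. That is fair if 15% is a genuine forecast. The protocol does not say how 15% was reached, which is why the fix offers two wordings.

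**Conclusion.** The point holds as a small arithmetic correction. On the protocol's own figures, 60 enrolled with 15% attrition gives 51 expected completers against a requirement of 52, and 60 tolerates at most 8 losses (13.3%). This much rests on no outside assumption.

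Two further statements are conditional. That 60 came from multiplying by 1.15 is an inference from an exact match. That the cost is about 0.8 percentage points of power depends on a two-sided t-test at d = 0.8, which is not in the documents. The point does not show that the trial is too small, and it does not bear on whether 26 per group was itself correctly derived.

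**What to change.** Change the one sentence in section 11.2, choosing the wording by what the 15% represents.

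- If 15% was only a description of the margin: state that 52 completers (26 per group) are needed and that enrolling 60 allows for up to 8 losses, about 13%.
- If 15% is the rate genuinely expected: keep it, and state that about 51 completers are then expected, one below the target of 52.

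Either wording also supplies the number needed to complete, which 11.2 currently omits. No power figure should be added there, because the stated sizing inputs do not support one.

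The cost is one sentence and a slightly less favourable stated margin. Enrolment, budget, procedures and analysis do not change.
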